### 12.2.3 Correlative/Exploratory Endpoints

- Genomic sequencing results will be either categorical variables (e.g., if from DNA sequencing), or continuous variables (e.g., if from RNA sequencing).
- PDL-1 status will be a binary variable (either positive or negative). Tumor mutation burden (TMB) is a continuous variable (e.g., the number of mutations per megabase [Mb] of the genome coding area (as per the Caris Life Sciences website)).
- Gut microbiome data will consist of continuous variables (i.e., diversity measures and composition measures). Common diversity measures are the  $\alpha$ -diversity and the Shannon diversity index. One composition measure is the between-community diversity (the  $\beta$ -diversity).

### 12.3 Study Design and Interim Analyses

An open label phase II study design of lenvatinib and pembrolizumab in metastatic NEPC is planned with primary endpoint of 6-month radiologic progression-free survival (rPFS), yes/no. For this binary endpoint, a 2-stage Simon near optimal design will be used, with these input parameters:  $p_0 = 0.10$ ;  $p_1 = 0.25$ ;  $\alpha = 0.125$ ; and power = 0.90. This results in the following design features:  $N_1 = 27$ ;  $R_1 = 2$ ;  $N = 40$ ;  $R = 6$ ;  $PET = 0.485$ ; and  $ASN = 33.70$ .

Hence, if there are at least 3 successes (patients who have had  $\geq 6.00$  months of rPFS) in the 27 patients in Stage 1 then the study will proceed to Stage 2, otherwise it will terminate early. If there are at least 7 successes in the final total of 40 patients, then the treatment will be considered promising. To allow for up to 20% of registered patients becoming non evaluable, up to 50 patients will need to be enrolled to yield 40 evaluable patients.

It may become necessary to temporarily suspend accrual at or near the completion of Stage 1 of the study in order to evaluate the 6-month rPFS (primary endpoint) of the last few Stage 1 patients. If Stage 1 accrual is at say, 24 patients and there have been no successes (i.e., no patients who have had  $\geq 6.00$  months of rPFS), then Stage 2 of accrual could not begin until up to 3 more patients are enrolled in Stage 1 and their rPFS outcome (success or not) has been determined.

Conversely, if  $\geq 3$  successes have been observed within the first 24 or fewer patients, then the interim analysis can be omitted, and accrual could continue into Stage 2 without interruption. There would be no need for a temporary suspension of accrual.

The study design operational characteristics were calculated using the “Two Stage Phase II Clinical Trials” program in the PASS (2019) software [10]. PET is the probability of early termination under the null hypothesis that  $p = 0.10$ . ASN is the average sample number, which is what is minimized in a Simon optimal (or near optimal) design. ASN is the mean number of patients required to complete a given Simon optimal (or near optimal) design after many hypothetical replications of the trial, wherein some trials terminated early (i.e., after Stage 1, with only  $N_1$  patients) and the others did not (i.e., went on to Stage 2, using a total of  $N$  patients).

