**PLEASE COMPLETE AND EMAIL A COPY TO HCRN**

## SYNOPSIS

TITLE	Phase II trial of Pembrolizumab and Lenvatinib in Advanced/metastatic Neuroendocrine Prostate Cancer [PLANE-PC]
SHORT TITLE	Pembrolizumab and lenvatinib in neuroendocrine prostate cancer
PHASE	II
OBJECTIVES	
Primary Objective Evaluate 6 month radiographic progression free survival (rPFS) rate with lenvatinib and pembrolizumab combination therapy in metastatic neuroendocrine prostate cancer (NEPC).
 
Secondary Objectives
 
 
• Assess the safety of pembrolizumab and lenvatinib combination therapy in metastatic neuroendocrine prostate cancer (NEPC).
 
• Assess overall survival (OS).
 
• Assess objective response rate (ORR).
 
• Assess duration of response (DoR).
 

STUDY DESIGN	An open label phase II study design of lenvatinib and pembrolizumab in metastatic NEPC is planned with primary endpoint of 6- month radiologic progression-free survival (rPFS) rate.
STATISTICAL CONSIDERATIONS	A 2-stage Simon near optimal statistical study design will be used for the binary primary endpoint of 6-month rPFS (yes/no). The design uses these input parameters: $p_0 = 0.10$ ; $p_1 = 0.25$ ; $\alpha = 0.125$ ; and $\text{power} = 0.90$ . If there are at least 3 successes in the 27 patients in Stage 1 the study will proceed to Stage 2, otherwise it will terminate early due to insufficient efficacy. If there are at least 7 successes in the final total of 40 patients, the treatment will be considered promising. To allow for up to 20% of registered patients becoming non evaluable, up to 50 patients will need to be enrolled to yield 40 evaluable patients. It may become necessary to temporarily suspend accrual at or near the completion of Stage 1 of the study in order to evaluate the 6-month rPFS (primary endpoint) of the last few Stage 1 patients.
TOTAL NUMBER OF SUBJECTS	N = 40 evaluable, Up to 50 total accrual

ESTIMATED ENROLLMENT PERIOD	Estimated 38 months of accrual.
ESTIMATED STUDY DURATION	Estimated 44 months to meet primary endpoint.

[figure not shown]

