### 12.2.2 Definition of Secondary Endpoints

- Safety of the combination will be assessed based on NCI Common Terminology Criteria for Adverse Events (CTCAE) version 5.0.
- Overall survival (OS) will be measured from Cycle 1 Day 1 to date of death from any cause. OS is further defined (including its censoring) in Section 9.8.3.
- ORR will be the proportion of patients achieving either a complete response (CR) or a partial response (PR), among all patients meeting the criteria of Section 12.6, as well as among all patients enrolled.
- DoR will be measured from the start date of the best response achieved until the date of relapse (i.e., progression). DoR is further defined (including its censoring) in Section 9.8.4. DoR applies to only the CR or PR patients.

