## 12.4 Analysis

### 12.4.1 Primary Objective

For the Primary objective (efficacy assessment), the binary endpoint (rPFS  $\geq$  6.00 months, yes/no) will be summarized with its point estimate (an occurrence rate), and 2-sided Wilson type 95% confidence interval (CI).

The duration of censored rPFS will be estimated with standard Kaplan-Meier (K-M) methodology. Point and CI estimates of the median and various timepoint-specific rPFS rates will be derived from the K-M life table (e.g., 6 month rate, 12 month rate, etc.), each with its own respective CI. A graph of the K-M curve for rPFS will be generated along with the Hall-Wellner 95% confidence band, and a display of the number of patients at risk at several time points, below the X-axis.

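### Does Section 12.3 count stage 1 in enrolled patients but the final total in evaluable patients, and so fall short of 90% power?

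*Combined protocol and SAP*

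**What the plan says.** The Synopsis and Section 12.3 give the same stage 1 rule. In the Synopsis it reads "If there are at least 3 successes in the 27 patients in Stage 1 the study will proceed to Stage 2". Neither place says whether those 27 are enrolled or evaluable.

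For the final decision, Section 12.3 says "If there are at least 7 successes in the final total of 40 patients, then the treatment will be considered promising". Here the unit is clear. The Synopsis lists "N = 40 evaluable, Up to 50 total accrual", and Section 12.3 allows for up to 20% of registered patients being lost, so that "up to 50 patients will need to be enrolled to yield 40 evaluable patients".

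Section 12.3 then illustrates when accrual might have to pause. The example opens "If Stage 1 accrual is at say, 24 patients and there have been no successes" and continues "then Stage 2 of accrual could not begin until up to 3 more patients are enrolled in Stage 1". The same sentence goes on to require that the six-month outcome of those further patients be known.

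Section 12.6 defines who is evaluable for efficacy: a patient who has had one cycle of treatment and disease imaging. For response rate, Section 12.2.2 gives two denominators, "among all patients meeting the criteria of Section 12.6, as well as among all patients enrolled". Section 12.4.1 names none for the primary endpoint.

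**The concern.** The example adds 3 enrolled patients to an accrual of 24, which makes 27 enrolled. The final 40 are evaluable. If the stage 1 look really took place at 27 enrolled, a 20% loss would leave 27 × 0.80 = 21.6 evaluable on average, with the bar still at 3 successes. A non-evaluable patient cannot supply a success, so the rule would be stricter than designed.

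This matters because stage 1 is the only efficacy rule that can end the trial early, and the design has no spare power. A stricter look would stop an effective treatment more often. Two analysts could also hold the look at different points, at 27 registrations or at about 34 (27 / 0.80 = 33.75).

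**Working it through.** **Inputs, all from Section 12.3.** Null rate 0.10, target rate 0.25, alpha limit 0.125, power 0.90; stage 1 size 27, stop at 2 or fewer; total 40, fail at 6 or fewer; printed early-stopping probability under the null 0.485 and average sample number 33.70; loss up to 20%.

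**1. Reproduce the plan with both totals in one unit.** Let X1 ~ Binomial(27, p) and X2 ~ Binomial(13, p).

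- Stop at p = 0.10: P(X1 ≤ 2) = 0.9^27 + 27(0.1)(0.9^26) + 351(0.01)(0.9^25) = 0.0582 + 0.1744 + 0.2520 = 0.4846 (printed 0.485).
- Average sample number: 27 + (1 − 0.4846) × 13 = 33.70 (printed 33.70).
- Probability of a promising result: the sum over x ≥ 3 of P(X1 = x) × P(X2 ≥ 7 − x). This is 0.0977 at p = 0.10 and 0.9001 at p = 0.25.
- Stop at p = 0.25: 0.0207.
- Enrolment: 40 / 0.80 = 50, as printed.

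**2. Compute the mixed count.** Take 27 enrolled at stage 1, each lost with probability d independently of outcome and not replaced before the look, and a final look at 40 evaluable. Stage 1 successes are then Binomial(27, (1 − d)p). At d = 0.20:

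- Stop at p = 0.10: P(X ≤ 2 | 27, 0.08) = 0.632.
- Stop at p = 0.25: P(X ≤ 2 | 27, 0.20) = 0.072.
- Averaging the two-stage sum over the number evaluable, n ~ Binomial(27, 0.80), with 40 − n in stage 2: type I error 0.0879, power 0.8687.

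| Loss | Stop at 0.25 | Power |
|---|---|---|
| 0% | 0.021 | 0.900 |
| 5% | 0.029 | 0.896 |
| 10% | 0.039 | 0.890 |
| 15% | 0.054 | 0.882 |
| 20% | 0.072 | 0.869 |

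With a fixed number evaluable at stage 1, power is 0.878 for 22 and 0.868 for 21.

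**3. Ask which count the printed figures belong to.** The mixed count leaves about 40 − 21.6 = 18.4 evaluable patients for stage 2, where the design has 40 − 27 = 13. With 22 or 21 evaluable at stage 1, the average sample number would be 28.84 or 27.68. Counting in enrolled patients throughout (27, then 50, with non-evaluable patients as failures) gives 27 + (1 − 0.632) × 23 = 35.47 at p = 0.10. None of these is 33.70. The printed figures require 27 and 40 in the same unit, and the Synopsis states the unit of the 40.

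**4. Check the surrounding text.** The Synopsis describes a stage 1 stop as one for lack of efficacy, Section 12.4.1 calls the primary analysis the efficacy assessment, and Section 12.6 says who is evaluable for efficacy. For response rate, all enrolled patients are named as an addition to the Section 12.6 set, which suggests that this set is the default. The 20% allowance applies to registered patients without limit to a stage, so stage 1 registrants are covered: about 34 registrations for 27 evaluable fits well within 50.

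**The case for a change.** The strongest case for a change is that the only text showing how to reach 27 counts enrolments, that nothing says a lost stage 1 patient is replaced, and that power is exactly at its target, so even 5% loss takes it to 0.896. In an open-label trial, fixing the unit after outcomes are visible would be poor practice.

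Part of this stands. The stage 1 rule does lack the word, and the example is loosely worded. The arithmetic of the mixed count is also right.

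It does not carry the conclusion. The example is offered as a hypothetical about pausing accrual; it does not define an analysis set. Its own sentence holds stage 2 back until outcomes are determined, so a patient with no determinable outcome does not naturally complete the 27. The 20% loss is the plan's ceiling. The loss of power also depends on loss being unrelated to outcome: if the 0.25 applies to everyone treated and those lost would have failed anyway, stage 1 successes remain Binomial(27, 0.25) and the wrong-stop probability stays at 0.021.

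A related question is which 40 count if a few more prove evaluable. Counting 43 with the bar at 7 would give a type I error of 0.128, above 0.125, but the rule is written for a total of 40, so that count would depart from the plan. If 39 were evaluable, power would be 0.886. These are unwritten details too, not errors.

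**Conclusion.** No change follows. Read coherently, both totals are evaluable patients as defined in Section 12.6, and the design has the power (0.900), early-stopping probability (0.485) and average sample number (33.70) that the plan prints.

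The shortfall to 0.869 is a conditional worst case. It needs a mix of units that the plan does not state, loss at the full 20%, loss independent of outcome, and no replacement before the look. Even then it costs about 3 points of power (0.900 − 0.869 = 0.031), and the type I error goes down, from 0.098 to 0.088. What remains is an unnamed unit and a loose example, a gap that the trial statistician would fill sensibly from the design calculation and the Synopsis.

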## 12.4 Analysis

### 12.4.1 Primary Objective

For the Primary objective (efficacy assessment), the binary endpoint (rPFS  $\geq$  6.00 months, yes/no) will be summarized with its point estimate (an occurrence rate), and 2-sided Wilson type 95% confidence interval (CI).

The duration of censored rPFS will be estimated with standard Kaplan-Meier (K-M) methodology. Point and CI estimates of the median and various timepoint-specific rPFS rates will be derived from the K-M life table (e.g., 6 month rate, 12 month rate, etc.), each with its own respective CI. A graph of the K-M curve for rPFS will be generated along with the Hall-Wellner 95% confidence band, and a display of the number of patients at risk at several time points, below the X-axis.

### 12.4.2 Secondary Objective

For the first Secondary objective (safety assessment), the analysis of toxicity rates will be performed using only the toxicity-evaluable (t-e) patients. All patients receiving at least one dose of study medication will be t-e.

The grade of each type of toxicity (an ordinal categorical variable) will be summarized with 1-way frequency distributions. Dichotomized versions (e.g., the occurrence rate of Grade 3-4 fatigue) will be summarized as described in Section 12.4.1 for a binary endpoint.

For the second Secondary objective (follow up for survival), OS will be analyzed in the same fashion as rPFS. See Section 12.4.1.

For the third Secondary objective (ORR assessment), ORR will be analyzed in the same fashion as 6-month rPFS rate. See Section 12.4.1, first paragraph.

For the fourth Secondary objective (DoR assessment), DoR will be analyzed in the same fashion as rPFS. See Section 12.4.1, second paragraph.

### 12.4.3 Exploratory Objectives

For the Exploratory objectives, all categorical variables will be summarized as described in Section 12.4.1. All continuous variables (e.g., number of mutations, or TMB, or gut microbiome diversity or composition measures) will be summarized with descriptive statistics including the point estimate of the mean, its associated 95% CI, standard deviation, median, inter-quartile range (IQR), minimum, and maximum.

The association of Exploratory correlative markers (whether binary, or ordinal categorical, or continuous) with a binary clinical outcome (e.g., the primary endpoint of achievement of rPFS  $\geq$  6.00 months, yes/no) will be explored using logistic regression models. Point and CI estimates of the odds ratio (OR) will be calculated, but the statistical interpretation will be limited to only the direction, magnitude, and precision of the association (i.e., the OR) as these are only exploratory analyses.

The same approach will be used to model clinical response (defined in Section 9.0) as a function of a given Exploratory correlative marker (e.g, TMB).

The association of Exploratory correlative markers (whether binary, or ordinal categorical, or continuous) with rPFS (or OS) will be explored using Cox proportional hazards (PH) regression models. Point and CI estimates of the hazard ratio (HR) will be calculated, but the statistical interpretation will be limited to only the direction, magnitude, and precision of the association (i.e., the HR) as these are only exploratory analyses.

### **12.5 Assessment of Safety**

All patients receiving one dose of study medication (lenvatinib or pembrolizumab) will be evaluable for safety assessment. National Cancer Institute (NCI) Common Terminology Criteria for Adverse Events (CTCAE 5.0 will be used to evaluate toxicity.

### **12.6 Assessment of Efficacy**

All patients receiving 1 cycle of study treatment (any amount of pembrolizumab and lenvatinib) and having had radiology imaging for disease assessment will be evaluable for efficacy.

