### 2.2 Endpoints

#### 2.2.1 Primary Endpoint

- Evaluate the clinical efficacy as defined by 6-month radiologic progression free survival rate (rPFS).
  - For soft tissue lesions, rPFS is defined as the date of Cycle 1 Day 1 to date of radiologic progression of soft tissue lesions per RECIST 1.1 or death whichever occurs first.
  - For bone lesions, rPFS is defined as the date of Cycle 1 Day 1 to date of progression of bone lesions per PCWG3 criteria or death whichever occurs first.

**NOTE:** the “date of progression” is the earlier date of either of those two possible types of progression.

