4: Chromogranin A, neuron specific enolase and urine NTx (optional) will be performed at screening/day 1 then prior to treatment every other Cycle starting at Cycle 3 Day 1 then at the D30 safety visit. PSA should be obtained at screening then prior to treatment every Cycle then at the D30 safety visit. Subjects that come off study without progression should have PSA obtained per investigator discretion. Testosterone will be performed at screening and at the D30 safety visit.

5: Tumor response assessment will consist of evaluation by CT scans of chest and MRI or CT of abdomen and pelvis. If a PET/CT is done for tumor assessment and if tumor/s are visible on the CT, this may be used for tumor evaluation. A bone scan will be obtained at screening and with other radiology imaging at the frequency as outlined below. An MRI of the brain should be performed at screening if there is a concern for the presence of brain metastases. Tumor imaging will be done at screening and every 3 cycles (9 weeks) for the first 12 cycles (36 weeks) and then every 4 cycles (12 weeks) until the patient is off study therapy (window of  $\pm$  1 week). Tumor imaging should follow week intervals in the case of study treatment delays due to toxicities. During follow up after completion of study treatment, imaging frequency is at the discretion of the site investigator. Imaging selected for each subject should remain the same throughout the study. Tumor imaging to be done at treatment discontinuation/safety follow up visit is at discretion of site investigator. If tumor assessments are available for subjects who have not yet experienced progressive disease (PD) at the time treatment is discontinued, the follow-up tumor evaluations will be documented in the eCRF until PD or death is confirmed, or until another treatment is initiated.

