### 9.8.2 Radiologic Progression Free Survival (rPFS)

rPFS has two components to its definition. For soft tissue lesions, rPFS will be measured from Cycle 1 Day 1 to date of radiologic progression per RECIST 1.1 or death from any cause, whichever occurs first. For bone lesions (non-measurable disease), rPFS will be measured from Cycle 1 Day 1 to date of progression per PCWG3 criteria [9] or death from any cause, whichever occurs first. Thus, the “date of progression” is the earlier date of either of those two possible types of progression. Subjects who have not progressed will be right-censored at the date of the last disease evaluation.

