## 12.2 Endpoints

### 12.2.1 Definition of Primary Endpoint

rPFS is defined as the date of Cycle 1 Day 1 to date of radiologic progression of soft tissue lesions per RECIST 1.1 or death whichever occurs first. rPFS is defined as the date of Cycle 1 Day 1 to date of progression of bone lesions (non-measurable disease) per PCWG3 criteria or death whichever occurs first. Censoring of rPFS is described in Section 9.8.2.

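### Section 12.6 makes no exception for death: if its imaging means an on-study scan, treated patients who die before that scan drop out of the final 40 and the 6-month rPFS rate is biased upward

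*Combined protocol and SAP*

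**What the plan says.** - **Evaluability (12.6).** After one cycle, for which any amount of pembrolizumab and lenvatinib suffices, patients "and having had radiology imaging for disease assessment will be evaluable for efficacy". The timing of the imaging is not given and death is not mentioned. This is the only definition of efficacy evaluability in the document.
- **Sample size and decision (12.3).** The design is p0 = 0.10, p1 = 0.25, alpha = 0.125, power = 0.90. It continues with at least 3 successes in 27 and is promising with at least 7 in 40. For the final number, "up to 50 patients will need to be enrolled to yield 40 evaluable patients", which allows for 20% becoming non-evaluable.
- **Stage 1 (12.3).** The 27 are described by accrual. In the worked example with 24 accrued and no successes, "then Stage 2 of accrual could not begin until up to 3 more patients are enrolled in Stage 1 and their rPFS outcome" is known.
- **Endpoint.** Death counts as an event in Section 2.2.1 ("date of radiologic progression of soft tissue lesions per RECIST 1.1 or death whichever occurs first"), in Section 9.8.2 ("date of radiologic progression per RECIST 1.1 or death from any cause, whichever occurs first") and, for bone lesions, in Section 12.2.1 ("per PCWG3 criteria or death whichever occurs first").
- **Scans (Section 7, footnote 5).** "Tumor imaging will be done at screening and every 3 cycles (9 weeks) for the first 12 cycles (36 weeks"), with a window of one week either side.
- **Analysis (12.4.1).** The binary rate is reported with a Wilson 95% interval, and "various timepoint-specific rPFS rates will be derived from the K-M life table". No population is named for either. For ORR, by contrast, 12.2.2 asks for a rate among all enrolled patients next to the rate in the 12.6 set.

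**The concern.** Every patient is scheduled for imaging at screening, so a condition that a screening scan could satisfy would select almost no one. That makes an on-study scan the natural meaning of 12.6. The 20% allowance points the same way: treatment must start within 5 business days of registration (Section 4) and any amount of both drugs meets the treatment condition, so it is hard to see where 20% would be lost unless the imaging condition removes patients after treatment has begun.

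On this reading, a treated patient who dies before an on-study scan has a known primary outcome, failure, yet does not count towards the 40, and another patient is enrolled to fill the place. All the patients removed this way are failures. The rate that decides whether the treatment is called promising is then too high whenever at least one such death occurs. If the 27 are also counted as evaluable patients, the Stage 1 futility stop is weakened as well.

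**Working it through.** **Inputs.** From 12.3: n1 = 27, r1 = 2, N = 40, R = 6, p0 = 0.10, p1 = 0.25, alpha ceiling 0.125. Assumed: d, the share of treated patients who die before any on-study scan. The documents do not give it; 0–10% is used as a range.

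**1. The plan's own figures.** Let X1 ~ Bin(27, p) and X2 ~ Bin(13, p).
- PET = P(X1 ≤ 2) at p = 0.10 = 0.0581 + 0.1744 + 0.2520 = 0.4846 (plan: 0.485).
- ASN = 27 + (1 − 0.4846) × 13 = 33.70 (plan: 33.70).
- P(promising) = Σ over x ≥ 3 of P(X1 = x) · P(X2 ≥ 7 − x). This is 0.0977 at p = 0.10 and 0.9001 at p = 0.25.
- Enrolment: 40 / (1 − 0.20) = 50.

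The design reproduces. The attained 0.0977 lies below the 0.125 ceiling.

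**2. Rate in the evaluable set.** Every excluded death is a failure, so successes are unchanged and the denominator shrinks: rate = p / (1 − d). For p = 0.10: 0.10/0.98 = 10.2%, 0.10/0.95 = 10.5%, 0.10/0.90 = 11.1%.

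**3. Type I error if p0 = 0.10 refers to all treated patients.** Two cases are needed, because the plan does not say whether 12.6 applies at Stage 1.
- *Case A, rule applied at both stages:* step 1 with p = 0.10/(1 − d).
- *Case B, rule applied to the final 40 only:* X1 ~ Bin(27, 0.10) among 27 treated patients; continue if X1 ≥ 3; the number of early deaths then dropped from Stage 1 is K ~ Bin(27 − X1, d/0.9); Stage 2 supplies 13 + K evaluable patients with success probability 0.10/(1 − d); promising if the total is at least 7.

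| d | Rate among evaluable | A: type I error | A: PET | B: type I error | B: PET |
|---|---|---|---|---|---|
| 0 | 10.0% | 0.098 | 0.485 | 0.098 | 0.485 |
| 2% | 10.2% | 0.106 | 0.470 | 0.105 | 0.485 |
| 4% | 10.4% | 0.115 | 0.456 | 0.114 | 0.485 |
| 5% | 10.5% | 0.120 | 0.448 | 0.118 | 0.485 |
| 10% | 11.1% | 0.147 | 0.410 | 0.142 | 0.485 |

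Solving for type I error = 0.125 gives d = 6.0% in case A and 6.5% in case B.

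**4. The cap of 50.** These calculations assume that 40 evaluable patients are always reached. A simulation of 400,000 trials with the cap gave 0.119 (d = 5%) and 0.147 (10%) in case A, and 0.118 and 0.142 in case B. At d = 10%, 1.0% (A) and 0.8% (B) of continuing trials fell short of 40, so the cap barely matters.

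**5. If p0 refers to evaluable patients only**, the success probability in that set is 0.10 by definition and type I error stays at 0.098 for any d.

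**6. At the decision boundary.** 7/40 = 17.5% (Wilson 95% CI 8.7–31.9%). With 2 left-out deaths, 7/42 = 16.7% of treated patients; with 4, 7/44 = 15.9% (7.9–29.4%).

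**The case against.** The link from 12.6 to the primary endpoint is inferred. Section 12.6 is cited by name only for ORR, the primary definition refers to 9.8.2 for censoring, and 12.4.1 names no population. The text never says post-baseline, footnote 5 counts screening among the tumor imaging, and protocols do contain redundant conditions. Because death is an rPFS event, a team working from the endpoint definition might simply score these patients as failures. Section 12.7 also speaks of obtaining the primary endpoint on all patients. And the effect may be small: ECOG 0–1 and a projected life expectancy of at least 6 months are required, and at d up to 5% the type I error stays below 0.125.

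Much of this stands as a condition on the finding. If a screening scan was meant, this bias does not arise. The share of early deaths is unknown. For scale only, exponential survival with the 15-month median quoted in Section 1.1 would give about 9% dead by week 9, but that median describes a background population, not patients selected as these are.

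It does not remove the problem. Section 12.4.1 labels the primary objective an efficacy assessment, 12.6 is the only rule for who is evaluable for efficacy, and 12.3 and the synopsis fix the final number in evaluable patients. The statement in 12.7 concerns the timeline and defines no analysis set. The Kaplan-Meier 6-month rate counts deaths as events, but its population is also unstated and it does not drive the 7-of-40 decision.

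**Conclusion.** This should be fixed. On the on-study reading of 12.6, the rule as written drops known failures from the rate that decides whether the treatment is promising. The direction of the bias is then certain. Its size depends on d: about 0.2 to 1.1 percentage points on a true rate of 10% for d between 2% and 10%.

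A rise in type I error needs a further condition, that p0 = 0.10 refers to all treated patients; whether 0.125 would be exceeded cannot be told from the documents. Weakening of the Stage 1 stop needs yet another, that the 27 are counted as evaluable patients. Confidence is medium, because the timing of the imaging and the tie between 12.6 and the primary analysis both rest on a reading of the text.

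**What to change.** 1. In 12.6, state whether the imaging must be post-baseline.
2. In 12.6 and 12.3, state that a patient who received any amount of both drugs and dies within 6 months of Cycle 1 Day 1 without an on-study scan is evaluable, counts as a non-success for the binary primary endpoint in both the 27 and the 40, and is not replaced.
3. Report the 6-month rPFS rate among all treated patients next to the rate in the 12.6 set, in line with what is already planned for ORR among all enrolled.
4. State which population p0 = 0.10 and p1 = 0.25 refer to.

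Items 1 and 2 remove the bias; items 3 and 4 make the result interpretable.

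The cost is a few sentences, with no new data and no added patients, and a slightly less favourable reported rate. If p1 = 0.25 was meant for scanned patients only, the rate among all treated is 0.25 × (1 − d), and power falls from 0.900 to 0.887 (d = 2%, rate 0.245), 0.866 (5%, 0.2375) or 0.822 (10%, 0.225). The sponsor would have to accept that loss or re-size the trial.
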